Of note, although this project does not include biopsy correlation, a separate small trial is being initiated at the San Francisco VA Medical Center in pre-prostatectomy patients to determine the sensitivity and specificity of nodal uptake seen on Ga-68 HBED-CC PSMA imaging. This will help to demonstrate the specificity of imaging uptake on the PET imaging.

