2.1 Primary

- Sensitivity and positive predictive value (PPV) on a per-patient and per-region-basis (Table 1) of ⁶⁸Ga-PSMA-11 PET for detection of tumor location confirmed by histopathology/biopsy.

Region	Description
1	Prostate Bed
2	Pelvis outside of prostate bed including lymph nodes
3	Extrapelvic soft tissue, lymph nodes and organ metastases (non-bone)
4	Bone metastases

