8.1 Study Endpoints

- Per patient and per region ⁶⁸Ga-PSMA-11 positivity.
- Biopsy correlation.

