8.2 Determination of Sample Size and Accrual Rate

8.2.1 Sample Size and Power Estimate

The primary endpoint is to evaluate the positive predictive value (PPV) on a (1) per-patient and (2) per-region-basis (prostate bed, pelvis, extrapelvic soft tissue, and bone metastases) of ⁶⁸Ga-PSMA-11 PET for detection of tumor location confirmed by histopathology/biopsy. Based on the results of previous studies, the following distribution of disease across the four regions are anticipated (19-21):

- a) Prostate bed: 30%
- b) Pelvis: 15%
- c) Extrapelvic soft tissue: 20%
- d) Bone metastases: 35%

It is anticipated that the PPV for the four regions and for all regions combined using conventional imaging ranges from 30-60%. An overall PPV for ⁶⁸Ga-PSMA-11 PET of at most 50% will be considered as unacceptably low. Hence, the null hypothesis that the PPV is at most 50% will be tested against the alternative hypothesis that the PPV is greater than 50%. It is hypothesized that ⁶⁸Ga-PSMA-11 PET imaging on the per-region and per-patient basis will substantially increase the PPV for the four regions to at least 70%. A sample size of 75 true positives is required for rejecting the null hypothesis that the PPV is at most 50% with 90% power at the one-sided 0.01 (=0.05/5 – a Bonferroni adjustment for evaluating the PPV for the four regions and for all regions combined) significance level, assuming an average regions specific prevalence of 20%. It is expected that approximately 25% of the accrued patients will undergo a biopsy. Hence, the proposed total number of patients requiring a biopsy is 375 in

order to power the analysis at a per region level. Assuming a prevalence rate of 20% for disease in each individual region, a total sample size of 1,500 patients is required. The following table shows the attainable power levels for detecting an increase in the PPV from 50% to 70% at the one-sided 0.01 significance level for the four disease regions and for all regions combined with the proposed sample size of 1500 patients:

Table: *Attainable power levels for detecting an increase in PPV from 50% to 70% with sample size of 1,500 patients (375 biopsies)*

	Prevalence	Number of Biopsies with True Positives	Power
Prostate bed	30%	113	98%
Pelvis	15%	56	78%
Extrapelvic soft tissue	20%	75	90%
Bone metastases	35%	131	>99%
All regions combined	100%	375	>99%

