^{68}Ga -PSMA-11 PET positive findings will be validated as true or false positive as outlined in more detail below. False negative ^{68}Ga -PSMA-11 PET findings cannot be determined as this would require biopsies of ^{68}Ga -PSMA-11 negative but conventional or functional non- ^{68}Ga -PSMA-11 PET positive imaging lesions. Inclusion of such patients however would be violation of the inclusion criteria.

^{68}Ga -PSMA-11 PET validation based on follow-up imaging:

- i) Lymph nodes will be assessed by change in size. ^{68}Ga -PSMA-11 positive lymph nodes will be considered:
 - (1) True positive:
 - If on follow-up imaging within 3-12 months, lymph nodes seen on CT or MRI decrease by more than 30% (for patients undergoing systemic treatment of focal therapy at this site) or increase by more than 20% in short axis diameter (with a minimum of 3 mm in change in size).
 - If patients with solitary lymph node regions show a decrease of PSA by greater than 50% after targeted treatment (i.e. external beam radiation) and the lymph nodes do not change in size (less than 30% decrease or less than 20% increase in short axis diameter).
 - (2) False positive:

- If on follow-up imaging within 3-12 months, sites of initial⁶⁸Ga-PSMA-11 positive lymph node lesions seen on CT or MRI decrease by more than 30% *without* systemic therapy or focal therapy at this site.
 - If ⁶⁸Ga-PSMA-11 positive lymph node lesions do not meet the criteria for above false positive or true positive findings.
- ii) Visceral lesions (non-lymph node soft tissue or organ) will be assessed by change in size. ⁶⁸Ga-PSMA-11 positive visceral lesions will be considered:
- (1) True positive:
- If on follow-up imaging within 3-12 months, visceral lesions seen on CT or MRI decrease by 30% (for patients undergoing systemic treatment of focal therapy at this site) or increase by 20% in largest diameter.
 - If patients with solitary visceral metastasis show a decrease of PSA by greater than 50% after targeted treatment (i.e. external beam radiation) and lesions do not change in size (less than 30% decrease or 20% increase in largest diameter).
- (2) False positive:
- If on follow-up imaging within 3-12 months, sites of initial⁶⁸Ga-PSMA-11 positive lymph node lesions seen on CT or MRI decrease by more than 30% *without* systemic therapy or focal therapy at this site.
 - If ⁶⁸Ga-PSMA-11 positive lymph node lesions do not meet the criteria for above false positive or true positive findings.

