- iii) ⁶⁸Ga-PSMA-11 positive bone lesions will be considered:
- (1) True positive:
- If there was a corresponding positive sclerotic lesion on the CT portion of the ⁶⁸Ga-PSMA-11 PET.
 - If there is focal uptake seen on the baseline bone scan performed within one month of ⁶⁸Ga-PSMA-11 PET.
 - If there is a lesion noted on the initial MRI performed within one month of ⁶⁸Ga-PSMA-11 PET.
 - If within 12 months follow-up CT demonstrates development of sclerosis.
 - If within 12 months follow-up MRI demonstrates a new bone lesion.
 - If within 12 months follow-up bone scan demonstrates new focal uptake.
- (2) False positive:
- If ⁶⁸Ga-PSMA-11 positive bone lesions do not meet the criteria for true positive findings.
- iv) ⁶⁸Ga-PSMA-11 positive prostate bed and prostate lesions will be considered:

(1) True positive:

- If on follow-up imaging within 12 months, lesions seen on CT or MRI decrease by 30% (for patients undergoing systemic treatment of focal therapy at this site) or increase by 20% in largest diameter..
- If patients with prostate bed lesions show a decrease of PSA by greater than 50% after targeted treatment (i.e. external beam radiation) and lesions do not change in size (less than 30% decrease or 20% increase in largest diameter).

(2) False positive:

- If on follow-up imaging within 3-12 months, sites of initial⁶⁸Ga-PSMA-11 positive lymph node lesions seen on CT or MRI decrease by more than 30% *without* systemic therapy or focal therapy at this site.
- If ⁶⁸Ga-PSMA-11 positive lymph node lesions do not meet the criteria for above false positive or true positive findings.

c) Histopathology/Biopsy:

- i) Localization of lesions for histopathology/biopsy will be classified according to the regions in table 1.
- ii) ⁶⁸Ga-PSMA-11 positive findings are aimed to be confirmed by histopathology/biopsy if clinically feasible.
- iii) Histopathological procedures and biopsies will be performed as clinically indicated and as per institutional protocol.

(1) Positive HP/Biopsy: Confirmed sites of metastatic or tumor involvement by histopathology/biopsy will be discussed with the responsible physician/surgeon.

(2) Negative Biopsy: Patients with suspected tumor recurrence on ⁶⁸Ga-PSMA-11 PET with negative histopathology/biopsy will be handled as outlined below:

(a) Lymph nodes:

- For patients undergoing nodal dissection: Patients will be rescanned with dedicated CT or MRI to determine if the suspicious ⁶⁸Ga-PSMA-11 positive node was removed.

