 1. If ⁶⁸Ga-PSMA-11 positive lymph node is still present, a repeat biopsy can be pursued if clinically feasible and applicable, or follow-up using imaging as described above will be performed.
 2. If the corresponding node was removed, then this will be considered a False Positive.
- For patients undergoing needle biopsy: Images of the procedure will be reviewed to determine if the correct node was biopsied.
 1. If the correct node was biopsied, then a negative biopsy will be considered a False Positive.

2. If the incorrect node was biopsied, then follow-up imaging as described above will be performed.
 - (b) Bone lesions: Given the high rate of false negative biopsies for osseous metastases in patients with prostate cancer, patients with negative bone biopsies of PSMA PET positive lesions will be further evaluated:
 - If pathology demonstrates an alternative diagnoses that is known to be PSMA positive (eg Renal Cell Carcinoma metastases, Paget's disease), then this will be considered a False Positive.
 - If pathology is indeterminate, then follow-up imaging as described above will be performed to determine if the lesion is a True Positive or False Positive.
 - (c) Additionally a repeat ^{68}Ga -PSMA-11 can also be obtained, as allowable, in addition to repeat conventional imaging (CT and/or MRI) in cases of negative biopsy to determine if the biopsy was true negative or false negative.
 - (d) Although not routinely performed during standard practice, immunohistochemical staining for PSMA of tumor specimens (primary and lymph node metastases) may be performed, although not required.

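### Histology-based sensitivity is a primary objective that 8.3.2 says cannot be determined, and the secondary accuracy plan conflicts on reference standard and population

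*Combined protocol and SAP*

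**What the plan says.** - **Objective.** Section 2.1, like the abstract, opens with "Sensitivity and positive predictive value (PPV) on a per-patient and per-region-basis (Table 1" and sets histopathology/biopsy as the reference.
- **Endpoint lists.** Sections 2.3.1 and 8.1 name "Per patient and per region ⁶⁸Ga-PSMA-11 positivity" and biopsy correlation. Neither names sensitivity or PPV.
- **Sizing and primary analysis.** Section 8.2.1 begins "The primary endpoint is to evaluate the positive predictive value (PPV" and gives no hypothesis, power or precision for sensitivity. The opening of 8.3.2 plans PPVs with Wilson intervals and nothing else.
- **False negatives.** Section 8.3.2 states that false negative "PET findings cannot be determined as this would require biopsies of" lesions that are PET-negative but positive on other imaging. The reason given is "Inclusion of such patients however would be violation of the inclusion criteria".
- **Background.** Section 1.2 says that "although this project does not include biopsy correlation, a separate small trial is being initiated", which conflicts with a primary aim based on biopsy.
- **Secondary accuracy.** Section 2.2 uses histology and conventional imaging follow-up as the reference for sensitivity, specificity, NPV and PPV. Section 8.3.3 uses that composite for PPV but histology alone for sensitivity, specificity and NPV. It also plans likelihood ratios and paired comparisons with conventional imaging.
- **Populations.** Section 8.3.1 gives patients with histology to the primary aim and all *remaining* patients to the secondary endpoints.

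**The concern.** Sensitivity needs a count of false negatives, and the primary analysis section says that count is not available. Either a declared primary objective goes unreported, or someone computes it later with a rule chosen after the data are seen.

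The second outcome is the worse one. Section 8.3.2 says that PSMA-11 "positive findings are aimed to be confirmed by histopathology/biopsy if clinically feasible", so tissue is sought mainly where PET is positive. Sensitivity in the histology set then tends to be too high, and the Wilson intervals in 8.3.3 express sampling error only, not this bias. Section 1.1 intends the data to be pooled across institutions for an NDA, so an undefined measure would carry into that submission.

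The secondary measures have the same weakness. With two reference standards, a population that excludes patients with histology if read literally, and no visible rule for PET-negative results, they could be computed in several incompatible ways.

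**Working it through.** **1. Can the primary objective be computed from the rules given?** Sensitivity = TP/(TP + FN). The follow-up rules in 8.3.2 (lymph nodes, visceral, bone, prostate bed) sort PET-positive findings into true and false positives. The histology rules deal with negative biopsies of PET-positive findings. The one mention of true and false negatives is repeat imaging "to determine if the biopsy was true negative or false negative", which describes the biopsy, not PET. So the visible text supplies TP and FP but neither FN nor TN.

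**2. Is the stated reason sound?** The criteria in 3.3.1 and 3.3.2 cover histology, PSA, performance status, age, consent, other therapy, tolerance of the scan, other malignancy and furosemide. None concerns findings on PET or conventional imaging. A patient with a PET-negative lesion seen on other imaging breaks none of them.

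**3. Does the sizing cover sensitivity?** One-sample normal approximation with the inputs of 8.2.1 (p0 = 0.50, p1 = 0.70, one-sided 0.01, power 90%):

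n = [(z0.99·√(p0(1−p0)) + z0.90·√(p1(1−p1)))/(p1−p0)]² = [(2.326 × 0.500 + 1.282 × 0.458)/0.20]² = 76.6, so 77 against the stated 75.

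Scaling: 75/0.20 = 375 biopsies and 375/0.25 = 1,500 patients, as stated. Power at 113, 56, 75 and 131 is 98.2, 76.7, 89.3 and 99.3%, against the stated 98, 78, 90 and >99%. The plan's figures reproduce within two patients and two points, from PPV inputs alone.

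**4. Secondary measures side by side.**

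| Item | Objectives and endpoints | Analysis sections |
|---|---|---|
| Reference for sensitivity, specificity, NPV | Histology and conventional imaging (2.2) | Histology only (8.3.3) |
| Population | No restriction stated | Patients without histology, read literally (8.3.1) |
| Per-region sensitivity | Abstract, 2.1, 2.2, 2.3.2 | None visible |
| PET false or true negative | Needed for sensitivity, specificity, NPV and likelihood ratios | No visible rule |

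Taken together, 8.3.1 and 8.3.3 ask for histology-only accuracy in patients who have no histology.

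**5. Possible size of the bias.** Let s be true sensitivity. Let PET-positive disease be verified at rate v and PET-negative disease at rate r·v. Then

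apparent sensitivity = s·v/(s·v + (1−s)·r·v) = s/(s + (1−s)·r).

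The documents give neither s nor r; both are assumed. The range for s takes in the detection rates cited in 1.2 (50% below PSA 1 ng/ml, above 85% above 2 ng/ml), which are not themselves sensitivities.

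| True s | r = 0.1 | r = 1/3 | r = 1 |
|---|---|---|---|
| 50% | 0.50/0.55 = 91% | 0.50/0.667 = 75% | 50% |
| 70% | 0.70/0.73 = 96% | 0.70/0.80 = 88% | 70% |
| 85% | 0.85/0.865 = 98% | 0.85/0.90 = 94% | 85% |

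These figures apply to the histology-only measure, not to the composite in 2.2.

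**6. Is follow-up imaging available to support a composite?** Section 8.3.2 plans conventional imaging at 3–12 months for all patients. Section 3.4 and the schedule in 6.1 show no imaging follow-up. Sections 3.5.1 and 3.5.2 put primary completion at 36 months and study completion at 48 (48 − 36 = 12), but the abstract has the study complete at three years. Section 8.2.2 describes accrual over four years, although 375/125 = 3. On the abstract's duration, or with four years of accrual, no 12-month tail remains.

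**The case against.** The best defence is that the operative plan is coherent for PPV. Section 8.2.1 names PPV as the primary endpoint, 8.3.2 analyses it and openly discloses the limit on false negatives, and 8.3.3 keeps per-patient sensitivity as a secondary summary. On that view the word sensitivity in 2.1 is a drafting remnant. The defence stands to this extent: the PPV hypothesis and its sizing are untouched, and sensitivity is not absent from the plan. It does not remove a primary objective that the analysis section says cannot be determined, nor the conflicts between 2.2, 8.3.1 and 8.3.3.

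A reader might infer several stronger things that the documents do not support:

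- *That histology-based sensitivity must be inflated, or will come out at 100%.* Section 8.3.2 also says biopsies are done as clinically indicated, and it foresees nodal dissection, which may sample PET-negative nodes. Inflation is likely, but it requires r < 1, and r is unknown.
- *That no biopsies will be taken at PET-negative sites, because the regional counts in 8.2.1 add up to all 375.* The counts are 375 times shares that sum to 100%, so they add to 375 by construction and say nothing about r.
- *That section 1.2 hands this trial's sensitivity question to another study.* The separate trial is in pre-prostatectomy patients, a different population. Only the remark on biopsy correlation conflicts.
- *That a rule for PET negatives exists nowhere.* The Appendix 2 flow chart is not fully shown, so the statement is limited to the visible text.

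**Conclusion.** The concern holds. Sensitivity against histopathology, per patient and per region, is a primary objective that cannot be met as written, and the inclusion-criteria reason given for this has no basis in section 3.3. The secondary accuracy measures conflict on reference standard and population, lack a visible rule for PET-negative results, and omit per-region sensitivity from the analysis.

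The contradiction rests on text alone and needs no assumption. The size of any bias is illustrative. It runs from none at r = 1 to 41 points (50% read as 91%) at s = 50% and r = 0.1; at s = 85% it is 13 points at r = 0.1 and 9 at r = 1/3. The primary-objective contradiction must be resolved before analysis. The background wording is a smaller matter.

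**What to change.** 1. In the abstract and 2.1, make PPV, per patient and per region, the only primary accuracy measure, and name it in 2.3.1 and 8.1.
2. Change 8.3.1 so that patients with histology are also in the secondary analysis set.
3. Keep sensitivity, specificity, NPV and likelihood ratios as secondary. Use the composite in 2.2 for the PET-only estimates and add per-region sensitivity to 8.3.3. Do not use the composite for the comparisons with conventional imaging, which would then be both comparator and part of the reference. Keep those histology-only and label them as subject to partial verification. Whether McNemar's test suits predictive values is a separate question.
4. Before analysis, define PET false negative, true negative and not evaluable for patients and for regions. Do not carry over the true-positive criteria of 8.3.2 unchanged: they were written for PET-positive lesions, and some rest on baseline imaging or PSA response. State how lesions that may have arisen after PET are treated. Report the number verified by PET result.
5. Limit the false-negative statement in 8.3.2 to the histology-only measure, correct the inclusion-criteria sentence, and correct the biopsy remark in 1.2.
6. Reconcile the imaging follow-up in 8.3.2 with 3.4 and the schedule in 6.1, and the durations in the abstract, 3.5.1, 3.5.2 and 8.2.2. Do not count on a 12-month tail until this is done.

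**Cost.** The sponsor gives up a primary sensitivity claim. PET-negative cases must be classified at all sites, and the plan must say which PET read counts for patients outside the primary set, since 8.3.2 provides central reading only for primary-endpoint data sets. Step 6 may change the schedule of procedures. An amendment with PRC and CHR approval is needed under 9.4. The PPV sizing does not change.

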8.3.3 Analysis of Secondary Endpoints

PPVs on a per-patient and per-region-basis of ^{68}Ga -PSMA-11 PET for detection of tumor location confirmed by histopathology/biopsy and conventional imaging follow-up will be calculated and reported along with the corresponding two-sided 95% confidence intervals. The paired McNemar's test will be used to compare the PPVs of ^{68}Ga -PSMA-11 PET imaging to the PPVs of conventional imaging.

Sensitivity, specificity, and NPVs on a per-patient basis of ^{68}Ga -PSMA-11 PET for detection of tumor location confirmed by histopathology/biopsy will be summarized in tabular format. Furthermore, the positive and negative likelihood ratios (LR+ and LR-) will be calculated and reported. Ninety-five confidence intervals of sensitivity, specificity, and NPV will be calculated using the Wilson score method. The comparisons of sensitivity, specificity, and NPV on a per-patient basis of ^{68}Ga -PSMA-11 PET imaging will be compared to of sensitivity, specificity, and NPV on a per-patient basis of conventional imaging using a paired McNemar's test.

Detection rates on a per-patient basis of ^{68}Ga -PSMA-11 PET stratified by PSA value (0.2 - <0.5, 0.5 - <1.0, 1.0 - <2.0, 2.0 - <5.0, 5.0) will be summarized in tabular format and compared between PSA strata using chi-square analysis. The impact of ^{68}Ga -PSMA-11 PET on clinical management in BCR patients will be evaluated using descriptive statistics.

9 Study Management

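### The two true-positive rules for lymph nodes do not meet, so some treated solitary nodes with a PSA response are scored false positive by default

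*Combined protocol and SAP*

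**What the plan says.** Section 8.3.2 b) i) gives a PET-positive lymph node two routes to true positive.

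- **Size route.** For shrinkage, the condition reads: "lymph nodes seen on CT or MRI decrease by more than 30% (for patients undergoing systemic treatment of focal therapy at this site". The scan must fall in a window of 3 to 12 months. For growth, the alternative condition is that nodes "increase by more than 20% in short axis diameter (with a minimum of 3 mm in change in size".
- **PSA route.** This is limited to a solitary nodal region. Such a patient has to "show a decrease of PSA by greater than 50% after targeted treatment (i.e. external beam radiation". A further condition on size must hold at the same time: "and the lymph nodes do not change in size (less than 30% decrease or less than 20% increase in short axis diameter".

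There are two false-positive bullets. One covers nodes that "decrease by more than 30% *without* systemic therapy or focal therapy at this site", so it cannot apply to a treated node. The other is residual: it takes any node for which "positive lymph node lesions do not meet the criteria for above false positive or true positive findings".

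The results feed section 8.3.3, where PPVs "confirmed by histopathology/biopsy and conventional imaging follow-up will be calculated and reported along with the corresponding two-sided 95% confidence intervals". The primary PPV in 8.3.2 rests on histopathology or biopsy, but the negative-biopsy pathway for nodes can return to the imaging rule: "If the incorrect node was biopsied, then follow-up imaging as described above will be performed". The same happens when the PET-positive node is still present after dissection and is not re-biopsied.

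**The concern.** The size route asks for a percentage and an absolute change. The PSA route closes once the percentage is reached, whatever the absolute change. A node that passes the percentage but not the 3 mm therefore leaves the PSA route without entering the size route, and the residual bullet makes it a false positive.

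For a shrinking node this reverses the evidence: with the same PSA fall, a somewhat better size response turns a true positive into a PET error, and a still better one turns it back. The visceral and prostate bed rules have the same two routes without a 3 mm minimum, and there the size and PSA limits meet. This suggests that the node minimum was added to one rule without adjusting the other.

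At stake is the composite PPV, per patient and for the two regions of Table 1 that contain nodes. Section 8.2.1 expects about 25% of 1,500 patients (375) to have a biopsy. The other 1,125 can be validated only through follow-up rules such as this one. Follow-up imaging is read locally, so sites could also resolve the wording differently and score the same node in opposite ways.

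**Working it through.** The plan gives no figure to reproduce here; the check is on the logic of the rules.

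**Inputs, all from 8.3.2 b) i).** Size route: decrease above 30% (treated) or increase above 20%, with a 3 mm minimum. PSA route: PSA fall above 50%, decrease below 30% or increase below 20%. Everything else: false positive. Consider a treated solitary node with a PSA fall above 50%, baseline short axis d mm and fractional shrinkage s.

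**1. Shrinkage, if the 3 mm covers both directions.** Size route: s > 0.30 and d × s ≥ 3. PSA route: s < 0.30. Neither holds when s ≥ 0.30 and d × s < 3, that is 0.30 ≤ s < 3/d. This band exists only if 3/d > 0.30, so d < 10 mm.

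| Baseline d | Shrinkage scored false positive |
|---|---|
| 4 mm | 30% to 75% |
| 5 mm | 30% to 60% |
| 6 mm | 30% to 50% |
| 8 mm | 30% to 37.5% |
| 9 mm | 30% to 33.3% |
| 10 mm or more | none, apart from exactly 30% |

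For d = 8 mm:
- to 6.0 mm: 2.0/8 = 25%, true positive by PSA;
- to 5.2 mm: 2.8/8 = 35%, but 2.8 mm < 3 mm, so false positive by default;
- to 5.0 mm: 3.0/8 = 37.5% and 3 mm, true positive by size.

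**2. Shrinkage, if the 3 mm covers increases only.** The 5.2 mm node passes the size route on 35% alone. The band in step 1 disappears.

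**3. Gaps under both readings.**
- Growth over 20% but under 3 mm, possible when 0.20 × d < 3, so d < 15 mm. For d = 8 mm: to 9 mm (+12.5%) is true positive by PSA; to 10 mm (+25%, 2 mm) is false positive; to 11 mm (+37.5%, 3 mm) is true positive by size.
- A decrease of exactly 30% (10 to 7 mm) is not more than 30% and not less than 30%. The same holds for an increase of exactly 20% (10 to 12 mm).

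**4. Possible size of the shrinkage gap.** The documents give no distribution of node size or shrinkage. Assume s uniform on 0-100% and d uniform from 4 mm to U mm, with U at least 10. The share in the band is

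∫ from 4 to 10 of (3/d − 0.30) dd, divided by (U − 4) = (3 ln 2.5 − 1.8)/(U − 4) = 0.949/(U − 4).

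- U = 10: 0.949/6 = 15.8%
- U = 16: 0.949/12 = 7.9%
- U = 20: 0.949/16 = 5.9%

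The denominator is treated solitary nodes with a PSA fall above 50%, not all PET-positive nodes. The figures apply only under the reading in step 1.

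**The case against.** The strongest reply is that the 3 mm bracket directly follows the increase limb and may qualify only that limb. Then the shrinkage case is a true positive by size. This stands as a possible reading, so one cannot say flatly that the plan scores shrinking small nodes as false positives. The wording of the bracket is neutral as to direction, however, and the PSA rule uses the same idea of size change for both directions, so the two-way reading is the more natural. The growth gap and the exact boundaries survive either way.

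A very literal reading of the word 'or' in the PSA rule would admit every shrinking node, because it has less than a 20% increase. That contradicts the requirement that the node be unchanged.

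A second reply is that the affected group is narrow: a solitary nodal region, targeted treatment, a PSA fall above 50%, and a change in a limited band. This also stands. Because the rules sit under the primary-endpoint heading, a reader might infer that the primary PPV is biased. Sections 8.3.1 and 8.3.2 tie that PPV to histopathology, and only the two biopsy-pathway exceptions reach the imaging rule.

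A reader might also infer that the loss falls where PSMA PET is meant to add most. The documents argue from sensitivity and from detection by PSA level, not by node size, so they do not support that.

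**Conclusion.** The defect holds as a failure of two stated rules to meet. Under both readings of the 3 mm minimum, some treated solitary nodes with a PSA response fall to the residual false-positive bullet. Under the two-way reading, these include nodes under 10 mm that shrink by more than 30% but less than 3 mm, for which both less and more shrinkage give a true positive.

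The direction is a downward bias in the secondary composite-reference PPV. That rests on taking the plan's own logic at face value: if a PSA fall with less shrinkage, and the same fall with more shrinkage, both count as tumour, the cases in between should too. These nodes have no histology, so they are supported by response evidence rather than proven.

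The number affected cannot be computed from the documents. The range of about 16%, 8% or 6% (baseline size uniform on 4-10, 4-16 or 4-20 mm) is illustrative. The top figure arises because the first size range excludes every node that the shrinkage gap cannot affect, and it should not be read as a share of all nodes or as a shift in PPV. The point merits correction before nodes are classified, but it does not threaten the primary analysis.

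**What to change.** In 8.3.2 b) i)(1), define an unchanged node in the PSA rule as one that does not meet the size criterion above it (the percentage and, where it applies, the 3 mm). In the same place, state whether the 3 mm minimum governs decreases, increases or both. Limiting it to increases would by itself remove the shrinkage gap, but not the growth gap or the exact boundaries, so the first change is needed in either case.

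With it, the 5.2 mm, 10 mm (from 8 mm) and 7 mm (from 10 mm) examples all become true positive by PSA, and no treated solitary node with a PSA response is left between the rules.

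The cost is one clause and one sentence, using size and PSA values that the rules already require. The downside is that a few nodes with growth under 3 mm and a PSA fall would count as true positive on the PSA evidence although they grew. A sensitivity analysis of the composite PPV can report those nodes separately.
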